There may be unforeseeable risks to the embryo or fetus, for both male and female subjects in this study. Subsequently, extreme care must be taken to avoid pregnancy in female subjects during this study for up to 30 days following completion of study treatment as well as in female partners of male subjects during this study for up to 90 days following completion of study treatment.

In addition to the risks listed above, there are risks that are not known or do not happen often when subjects take TAF, including severe or life-threatening allergic reactions, or interactions with another medication. Subjects will be informed in a timely manner, both verbally and in writing of any new information or changes to the way the research will be done that might influence their willingness to continue to take part in this study.

For more details on adverse reactions please see the Vemlidy® package insert for more information.

Benefits: The medical knowledge gained may be able to guide future research, clinical trial planning, and guideline recommendation for this patient population.

3. Study Overview

Dosage regimen: Patients on any antiviral treatment for chronic HBV who plan to be switched by their physician to be treated with TAF 25 mg for 24 months will be enrolled. Any treatment after will be up to the physician's discretion. The drug will be administered orally, per manufacturers' instructions, and can be taken with food.

Compliance: Patients will be enrolled and monitored according to the protocol, GCP, and clinical practice guidelines.

Study population: Approximately 251 adult patients currently on antiviral therapy and are planned to be switched to TAF by their physicians will receive TAF 25 mg. Enrollment goal will be approximately 185 for prior entecavir patients, 33 for prior tenofovir (TDF) patients and 33 for prior combination therapy patients (any oral nucleos(t)ide combination). Enrollment goal for entecavir is based on relative lack of data for sequential entecavir to TAF therapy. Enrollment goal for TDF is used to avoid bias and as a comparison. Enrollment goal for combination therapy is based on estimates of the small patient population with CHB maintained on long term combination therapy.

Inclusion criteria:

1. Male or female, age ≥ 18 years
2. CHB diagnosis confirmed by positive HBsAg or HBV DNA or HBeAg or documented history of CHB in physician note

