- To describe trends in serum creatinine and calculated creatinine clearance as available by local labs.
- To describe trends in bone mass from baseline to 24 months after switch.

5. Study Design

Study design: Open label prospective interventional cohort study.

Study Timelines:

[figure not shown]
- Total study duration: 36 months
- Study Start-Up: 3 months
- Patient enrollment: 6 months
- Patient follow-up: 24 months
- Final analysis & Manuscript Preparation: 3 months
- Publication plan: Interim analysis 2018 – 2019, Final analysis 2020

Primary endpoint: Rate of viral suppression at 6, 12, 18, 24 months after switch, as available.

Secondary endpoints(s):

- ALT levels at 6, 12, 18, 24 months after switch
- Serum creatinine, calculated creatinine clearance (Cockcroft-Gault) at 6, 12, 18, 24 months after switch
- % change in bone mineral density from baseline to 24 months after switch

Study schematic:

Study protocol: Treatment Outcomes in Chronic Hepatitis B Patients on Sequential Therapy with Tenofovir Alafenamide

The following table below describes all study procedures:

Study protocol: Treatment Outcomes in Chronic Hepatitis B Patients on Sequential Therapy with Tenofovir Alafenamide

Study Procedures	Screening/Baseline	Treatment Months*							
		3*	6	9*	12	15*	18	21*	24/ED
Informed Consent	X								
Inclusion/ Exclusion Criteria	X								
Medical History ¹	X								
Vital Signs	X		X		X		X		X
Physical Examination	X		X		X		X		X
Adverse Events			X		X		X		X
Concomitant Medications	X		X		X		X		X
Bone Density Scan (DEXA) ^{4,5}	X								X
HBeAg ²	X		X		X		X		X
HBV DNA PCR	X	X	X	X	X	X	X	X	X
α -fetoprotein (AFP)	X		X		X		X		X
Ultrasound (to rule out HCC)	X		X		X		X		X
International Normalized Ratio (INR) ³	X				X				X
CBC Panel with WBC, Hb, Platelet, HCT	X		X		X		X		X
Complete Metabolic Panel with Na, K, Cr, Tb, CO2/HCO3, BUN, GLU, AST, ALT, ALK, ALBU	X	X	X	X	X	X	X	X	X
Serum Phosphorus	X	X	X	X	X	X	X	X	X
Fasting Cholesterol Panel with Total Cholesterol, HDL, direct LDL, TG	X		X		X		X		X
Vitamin D Assessment	X								
Fibrotest, Fibrosure, Fibrospect, FIB-4 or Elastography	X								
HCV, HDV, HIV Testing ⁶	X								
Urinalysis	X	X	X	X	X	X	X	X	X

Study protocol: Treatment Outcomes in Chronic Hepatitis B Patients on Sequential Therapy with Tenofovir Alafenamide

Data capture/case report forms	X		X		X		X		X
Study Drug Dispensing	X		X		X		X		X

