If a specific medical diagnosis has been made, that diagnosis or syndrome should be recorded as the adverse event, whenever possible. However, a complete description of the signs, symptoms and investigations which led to the diagnosis should be provided. For example, if clinically significant elevations of liver function tests are known to be secondary to hepatitis, "hepatitis" and not "elevated liver function tests" should be recorded. If the cause is not known, the abnormal test or finding should be recorded as an adverse event, using appropriate medical terminology (e/g/ thrombocytopenia, peripheral edema).

Maintenance of Safety Information: Safety information will be maintained in a clinical database/repository in a retrievable format. At a minimum, at the end of the treatment phase ("last patient off treatment") as well as the end of the follow-up phase ("last patient out") of

the study, [name] shall provide all adverse events, both serious and non-serious, in report format.

Reporting Timelines: All safety information covered in SAEs should be reported within **24 hours** of becoming aware of the event(s) to the sponsor. All non-serious AEs should be recorded in a CRF and reported to the site's IRB as per their guidelines for prompt reporting.

Pregnancy Precaution and Contraceptive Requirements: Because the full effects of TAF on an unborn baby or a nursing infant are not known, any female who is pregnant or breast feeding an infant will not be enrolled in this study. Female subjects must also refrain from egg donation and in vitro fertilization during treatment and until at least 30 days after the end of relevant systemic exposure.

If a subject becomes pregnant or suspects that they have become pregnant while in the study or within 30 days after the last dose of study drug, they must stop taking all the study drugs and notify their study doctor immediately. They will be discontinued from the study. If their partner becomes pregnant while they are in the study, the subject must notify the study doctor immediately. The study doctor will request to track the pregnancy and will report the pregnancy to the Study Sponsor.

If a subject is a sexually active female, it is required that they use an effective method of birth control from the Screening/Baseline visit as well as during the study and for at least 30 days after stopping the last dose of study drug. Effective protocol specified methods of birth control in this study are as follows:

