Complete abstinence from intercourse of reproductive potential or consistent and correct use of 1 of the following methods of birth control listed below:

- Intrauterine device (IUD) with a failure rate of < 1% per year
- Intrauterine hormone-releasing system (IUS) with a failure rate of < 1% per year
- Tubal sterilization
- Essure micro-insert system (provided confirmation of success 3 months after procedure)
- Vasectomy in the male partner (provided that the partner is the sole sexual partner and had confirmation of surgical success 3 months after procedure)
- Barrier methods (one female barrier and one male barrier must be used in combination)
 - Female barriers: Diaphragm with spermicide or Cervical cap with spermicide
 - Male barriers: Male condom (with or without spermicide)
- Hormonal methods
 - Oral contraceptives (either combined or progesterone only)
 - Injectable progesterone
 - Implants of levonorgestrel
 - Transdermal contraceptive patch

-Contraceptive vaginal ring

During the study, male subjects with female partners of childbearing potential should use condoms when engaging in intercourse of reproductive potential.

Birth control methods that are unacceptable include periodic abstinence (e.g., calendar, ovulation, symptothermal, post-ovulation methods), withdrawal (coitus interruptus), spermicides only, and lactational amenorrhea method (LAM). Female condom and male condom should not be used together.

8. Statistics

Data management and analysis will be performed at Stanford.

Sample size to be used in the analysis: Sample size will be estimated by enrollment feasibility at all study sites.

Statistical methods to be employed: Descriptive and comparative statistics will be performed for all demographic and clinical variables that are outcome endpoints for this pilot study.

Level of significance: A 95% confidence interval will be used.

Termination of trial: Termination of the trial will be upon completion of follow-up of all 251 subjects enrolled and/or up to the discretion of the sponsor, [name].

Procedure for missing, unused, spurious data: Data that is missing, unused or spurious data will all be treated as missing data. This data will be marked as an empty field.

Deviation from original statistical plan: Any deviation from the original statistical plan will be up to the discretion of the study sponsor.

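### The 90-day pregnancy precaution for partners of male subjects is not written into the Section 7 condom rule, and the partner-notification rule should be aligned with it

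*Combined protocol and SAP*

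**What the plan says.** The summary of known and potential risks, just before Section 3, sets two periods in one sentence. Extreme care is required to "avoid pregnancy in female subjects during this study for up to 30 days following completion of study treatment", and likewise in "female partners of male subjects during this study for up to 90 days following completion of study treatment".

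Section 7, under Pregnancy Precaution and Contraceptive Requirements, turns these into instructions.

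- **Women, pregnancy notification:** applies "while in the study or within 30 days after the last dose of study drug".
- **Women, birth control:** required from the Screening/Baseline visit, "as well as during the study and for at least 30 days after stopping the last dose of study drug".
- **Men, condoms:** "During the study, male subjects with female partners of childbearing potential should use condoms when engaging in intercourse of reproductive potential".
- **Men, partner pregnancy:** "If their partner becomes pregnant while they are in the study, the subject must notify the study doctor immediately". The study doctor then asks to track the pregnancy and reports it to the sponsor.

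Exclusion criterion 9, which covers willingness of both sexes to use contraception, also refers only to the time of the study. The 90 days appears nowhere outside the risk summary.

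**The concern.** A precaution in a risk summary works only if the instructions that sites follow carry the same period. For women they do. For men the condom rule names no time after treatment, although the risk summary gives partners of men the longer period of the two. A coordinator who counsels men from Section 7 alone could reasonably tell a man finishing at Month 24 that condoms are no longer required.

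Section 7 itself says that the full effects of TAF on an unborn baby are not known, which explains why partner pregnancies are to be tracked. If the reporting duty ends when the man leaves the study, a pregnancy inside the protocol's own precaution window might not reach the study doctor.

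**Working it through.** The protocol gives no calculation to reproduce here. The check compares the stated periods and then asks how far being in the study could reach.

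**1. Stated periods after treatment**

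| | Risk summary (avoidance) | Section 7, contraception | Section 7, notification |
|---|---|---|---|
| Female subjects | 30 days | 30 days | 30 days |
| Partners of male subjects | 90 days | none stated | none stated |

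The 30 or 90 days is written into 2 of 2 rules for women and 0 of 2 for men. Only the contraception column puts the avoidance period into effect. The risk summary says nothing about reporting, for either sex.

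**2. Upper bound of the condom gap**

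90 days (risk summary) − 0 days (Section 7) = 90 days. This applies to a man who stops TAF at Month 24 if being in the study ends there. Section 5 supports that reading:

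- The schedule of procedures ends at Month 24 or early discontinuation (ED).
- The timeline lists "Patient follow-up: 24 months" and "Total study duration: 36 months". Start-up 3 + enrollment 6 + follow-up 24 + final analysis 3 = 36 months, so no time is set aside for follow-up after Month 24.
- The women's notification rule lists time in the study and 30 days after the last dose as separate periods. So being in the study does not, by itself, supply a post-dose window.

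**3. Lower bound**

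- Section 5 puts participation at about 2.5 years. 2.5 × 12 = 30 months, and 30 − 24 = about 6 months after treatment. That exceeds 90 days, so the gap is nil on this reading. It does not fit the timeline for the last man enrolled: entry at month 3 + 6 = 9, and 9 + 30 = month 39, which is 3 months past the stated 36.
- Section 7, Maintenance of Safety Information, names a follow-up phase apart from the treatment phase. This too could extend being in the study, by a length it does not give.
- Section 6 gives early withdrawals a visit 3 to 6 months after the ED visit. Three months is about 91 days, so the gap is nil for them if they count as in the study until that visit and the ED visit is at or after the last dose. Completers have no such visit.

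The range is therefore 0 to 90 days per man. The number of men is not given.

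**4. Other routes to a report**

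Section 7 requires serious adverse events to be reported up to 30 days after the last dose. That concerns the subject's own events and stops 60 days short of day 90 (90 − 30).

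**5. Where a 90-day window falls**

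The last man enrolled enters at about month 9 and finishes treatment at 9 + 24 = month 33. Ninety days is about 3 months, so his window closes at about month 36, the planned end of the study. There is no slack.

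**The case against.** The strongest reply is that nothing is contradicted. The risk summary is itself mandatory, so a site that reads the whole protocol already has the 90-day duty. The condom rule does not say that condoms are needed only during the study. A reader might infer that sites would necessarily apply a shorter condom period. The documents do not support that: the risk summary binds too, and being in the study may run past treatment. What stands is that the risk summary names no method, the condom rule names no later period, and the women's rules show how the drafters wrote a post-dose period when they stated one.

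A reader might also infer that the partner-notification rule conflicts with the 90 days. It does not, because the risk summary sets a period for avoiding pregnancy and none for reporting it. Extending the rule is reasonable only by analogy with the women's notification rule.

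A third inference would be that men are never told of a later duty. Consent pages were removed before this review, and the participant information may give the period, so this cannot be judged here.

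Finally, the starting points differ. The risk summary counts from completion of study treatment and the women's Section 7 rules from the last dose of study drug. Section 3 leaves treatment after 24 months to the physician, so the two can diverge for a man who continues TAF. That objection stands, and the fix has to deal with it.

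**Conclusion.** The point holds as a minor gap in safety wording. The protocol sets a 90-day avoidance period for partners of men, and the Section 7 condom rule that puts it into effect states no time after treatment. The shortfall is up to 90 days for a man who stops TAF at Month 24, and may be nil if being in the study is read to extend beyond treatment. Lack of a post-treatment period in the partner-notification rule is a matter of alignment.

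This rests on two assumptions: that 90 days is the intended period, and that the participant information does not already settle the matter. No endpoint, sample size or analysis is affected.

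**What to change.** First, the sponsor should confirm that 90 days is intended. Then:

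1. **Condom rule, Section 7.** After the opening words During the study, insert: *and for 90 days after the last dose of study drug*.
2. **Partner-pregnancy rule, Section 7.** After the reference to being in the study, insert: *or within 90 days after the last dose of study drug*. Present this as matching the women's notification rule.
3. **Starting point.** State that the period runs from the last dose of study drug, as in the women's rules. Define that dose for Japan sites, where Section 5 says TAF is prescribed and insured, not supplied, and for men who continue TAF after Month 24.
4. **Participant information.** Check that it gives the same periods.

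The cost is two short insertions and a definition, up to 90 more days of condom use and reporting duty for men, and the check of the participant information. No extra visit is needed, because the subject makes the notification. A reader might suppose from the 36-month timeline that every report would arrive before the planned end. For the last men enrolled it may not: their window closes at about month 36, a pregnancy late in it would be recognised afterwards, and tracking to outcome would run later still. The sponsor should plan to receive some reports after that date.

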Prior and Concomitant Medications

Medications not permitted before and during the study treatment phase will be up to the discretion of the treating physician. Disallowed concomitant medications include:

- Drugs that reduce renal function or compete for active tubular secretion may increase concentrations of tenofovir and the risk of adverse reactions (e.g., cidofovir, acyclovir, valacyclovir, ganciclovir, valganciclovir)
- Nephrotoxic agents (e.g., aminoglycosides, amphotericin B, vancomycin, cidofovir, foscarnet, cisplatin, pentamidine, cyclosporine, tacrolimus)
- Other products containing TAF
- Oxcarbazepine, phenobarbital, phenytoin, rifabutin, rifampin, rifapentine, or St. John's wort. Such co-administration is expected to decrease the concentration of TAF, reducing the therapeutic effect of TAF.
- Drugs that strongly affect P-gp and BCRP activity may lead to changes in TAF absorption.

Monitoring subject compliance: Patients will be encouraged by their physician to adhere to clinical and lab visitation recommendations per routine clinical care.

Measures to minimize/avoid bias: Not applicable. This study does not include randomization of subjects or blinding.

Description of study treatment: See Dosage regimen in Section 3 (Study Overview).

Duration of subject participation: Patient participation is expected to take approximately 2.5 years. Study treatment period, continuation and choice of therapeutic agents are at the discretion of the local primary investigator and treating physician and patient.

Discontinuation criteria: The study can be terminated at any time for any reasons with written notice by [name] (Study Sponsor). For discontinuation criteria for individual subjects, see Withdrawal criteria in section 6 (Selection and withdrawal of subjects). Though there are no formal treatment stopping rules in this study, patients will be asked to stop early if there are any adverse events that the investigator feels make it the patient's best interest to stop treatment.

Accountability procedures for TAF:

U.S.A, S. Korea and Taiwan Sites

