- Failure to follow study instructions or protocol violation (subject to investigator)
- Adverse events (subject to investigator)
- Any medical, psychosocial or administrative or other reasons that would, in judgment of the investigator, be detrimental to the patient's well-being.
- Death
- Withdrawal of informed consent – They may be considered withdrawn if they state an intention to withdraw or fail to return for study visits, or become lost to follow-up for any other reasons.

Procedures for Subject Withdrawal:

When and how to withdraw subjects from trial: Subjects will be withdrawn during the study at any time if they meet any of the withdrawal criteria above. If premature withdrawal occurs for any reason a report will be generated by investigator describing reasons and nature of the withdrawal and will include documentation of last patient encounter and laboratory testing prior to or at time of withdrawal. If patient stops the study treatment early, documentation outlining the reasoning will be drawn.

Data to be collected for withdrawn subjects: For patients not lost to follow-up, viral suppression and pertinent clinical and laboratory data to be collected will be those which are done as part of standard clinical care including bone and renal function tests.

Follow-up for subjects withdrawn from investigational product: If patients are withdrawn from the study early, they will complete an Early Discontinuation (ED) Visit, during which they will have a physical exam, review their concomitant medication and any adverse events, review their drug accountability, and complete any routine laboratory, bone density or imaging tests. All patients that have withdrawn from the study early will also complete a follow-up visit 3 to 6 months after their ED visit.

7. Adverse Events and Toxicity Management

Assessment of safety: Safety assessments will include monitoring of laboratory results, vital signs, treatment emergent adverse events, serious adverse events, etc. Safety assessments will be performed at every clinic visit as part of clinical care and during follow-up visits.

Adverse events definitions:

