For each subject, AEs and SAEs should be recorded after informed consent is obtained until the subject has completed participation in the study as follows:

- A serious adverse event must be reported if it occurs during a subject's participation in the study and within **30 days** of receiving the last dose of study drug.
- Any serious adverse event that is ongoing when a subject completes his/her participation in the study must be followed until any of the following occurs:
 - The event resolves or stabilizes;
 - The event returns to baseline condition or value (if a baseline value is available);
 - The event can be attributed to agents(s) other than the study drug, or to factors unrelated to study conduct.

Recording of Adverse Events, Serious Adverse Events: Recording should be done in a concise manner using standard, acceptable medical terms. The adverse event recorded should not be a procedure or a clinical measurement (i.e. a laboratory value or vital sign) but should reflect the reason for the procedure or the diagnosis based on the abnormal measurement. Preexisting conditions that worsen in severity or frequency during the study should also be recorded (a preexisting condition that does not worsen is not an adverse event).

Furthermore, a procedure or surgery is not an adverse event; rather, the event leading to the procedure or surgery is considered an adverse event. Any event requiring in-patient hospitalization that occurs during the course of a subject's participation in a trial must be reported as an SAE. Hospitalizations that do not meet the criteria for SAE reporting are:

- Reasons described in the Protocol, e.g. drug administration, Protocol-required testing
- Surgery or procedure planned prior to entry into the study.

If, in [name] judgment, a clinical significant worsening from baseline is observed in any laboratory or other test parameter, physical exam finding, or vital sign, a corresponding clinical adverse event should be recorded.

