Selection of subjects to be included in analyses: All eligible subjects that have not been withdrawn from the study will be included in analyses.

9. Direct Access to Source Data/Documents

PIs at local centers will have access to their corresponding source documents. [name] and central coordinators will have access to de-identified source documents from all clinical sites and will conduct study related monitoring and audits as necessary. All participating centers will allow for IRB review and regulatory inspections of documentation by providing

access to the source data/documents. All participating centers will also transmit de-identified source documents to central coordinators for review.

10. Quality Control and Quality Assurance

[name] will ensure quality control and quality assurance by:

- a. Periodic coordinator conference calls and investigator conference calls as needed.
- b. In-person investigator meetings 1-2 times a year: APASL (Feb) or EASL (April), and AASLD (October).

One of [name] staff will conduct monitoring visits at each non-Stanford location after enrollment of each site's first patient and before closure of the study to resolve all queries. Additional monitor visits may be carried out during the duration of the study, based on [name] discretion. Within reasonable notice, site PI and research staff will agree to provide desk space for central coordinator site visits and will cooperate in providing needed source documents for the purpose of data monitoring.

11. Ethics

The study will be approved by each site's institutional review board (IRB) to comply with ethical conduct guidelines and has been registered on <http://www.ClinicalTrials.gov>, as required by U.S. Law.

12. Data Handling and Recordkeeping

Each patient is uniquely identified in the study by a combination of the center ID and patient number. The center ID is assigned by the sponsor, [name]. The patient number is generated after record is deemed eligible and all data in the CRF is submitted to the central coordinator. This identification code will be used for the duration of the study. Information linking this identification code to the patient will be kept on a password protected file stored securely at each local site.

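### All analyses leave out withdrawn subjects, so a patient withdrawn with renal decline may be missing from the creatinine and clearance summaries

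*Combined protocol and SAP*

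**What the plan says.** Section 8 (Statistics), on selection of subjects for analysis, reads: "All eligible subjects that have not been withdrawn from the study will be included in analyses". It makes no exception by endpoint. The plan has no safety set, on-treatment rule, imputation or sensitivity analysis that would bring withdrawn subjects back. Section 8 says only that missing data are left as empty fields.

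The renal endpoint is secondary (Section 5): "Serum creatinine, calculated creatinine clearance (Cockcroft-Gault) at 6, 12, 18, 24 months after switch".

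Three provisions link renal decline to withdrawal:

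- Section 7 asks for an adverse event to be recorded when, in the responsible physician's judgment, "a clinical significant worsening from baseline is observed in any laboratory or other test parameter".
- Section 5, under discontinuation criteria, says "patients will be asked to stop early if there are any adverse events"; the sentence goes on to make this depend on the investigator's view of the patient's interest.
- Section 6 lists among the withdrawal criteria "Adverse events (subject to investigator").

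Section 6 also provides for data on withdrawn patients. For those not lost to follow-up, the data to be collected are "those which are done as part of standard clinical care including bone and renal function tests". At an early discontinuation (ED) visit they "complete any routine laboratory, bone density or imaging tests". It then adds: "All patients that have withdrawn from the study early will also complete a follow-up visit 3 to 6 months after their ED visit".

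**The concern.** The renal endpoint can influence who is counted in it. A fall in clearance may become an adverse event, the adverse event may lead to withdrawal, and withdrawal removes the patient from the analyses. Read literally, the Section 8 sentence removes the whole subject, including creatinine values measured before withdrawal. The protocol thus collects renal data on these patients and then excludes them from the renal summaries.

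This matters because the background text gives a possibly lower renal risk than with TDF as part of the case for TAF. Inclusion criterion 5 admits men with clearance just above 15 ml/min and women just above 12.75 ml/min, so some renal withdrawals are plausible. A trend computed only on patients who were not withdrawn could make renal function after the switch look better than it was.

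**Working it through.** **Planned size.** Section 3 gives cohort goals of 185 (entecavir), 33 (TDF) and 33 (combination): 185 + 33 + 33 = 251, which agrees with the stated total. The documents give no withdrawal rate, rate of renal decline or standard deviation, so everything below is illustration under assumed inputs.

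**Effect on mean change in clearance.** Assume 5 of 251 patients lose 50% of clearance and the others average no change. If w of the five are withdrawn and nobody else is, the mean among those analysed is -50 × (5 - w) / (251 - w):

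| w | Calculation | Mean change (percentage points) |
|---|---|---|
| 0 | -250/251 | -1.0 |
| 3 | -100/248 | -0.4 |
| 5 | 0/246 | 0.0 |

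**When bias arises.** If the same share p of decliners and of the others is withdrawn, the mean is -50 × 5(1 - p) / [251(1 - p)] = -250/251, unchanged. Exclusion flatters the trend only if decliners are withdrawn more often than others.

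**Range in mL/min.** Let k patients of N be withdrawn with mean change d, and let retained patients average 0. The rule reports 0.0; including the withdrawn patients gives k × d / N.

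- Overall, with 3 to 13 patients (about 1% to 5% of 251) and d from -15 to -25: 3 × (-15)/251 = -0.2 to 13 × (-25)/251 = -1.3 mL/min.
- In a cohort of 33, with 1 to 3 patients: 1 × (-15)/33 = -0.5 to 3 × (-25)/33 = -2.3 mL/min.

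**Against sampling error.** Assuming a standard deviation of change of 10% to 15%, the 95% half-width at n = 251 is 1.96 × 10/√251 = 1.2 to 1.96 × 15/√251 = 1.9 percentage points. The 1.0-point shift lies inside that.

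**The case against.** **Stopping TAF is not the same as leaving the study.** Section 8 excludes subjects withdrawn from the study, whereas the Section 5 sentence concerns stopping treatment. Section 6 documents the two separately, and Section 5 leaves continuation and choice of drug to the physicians and the patient. A reader might infer that any patient stopped for renal decline leaves the summaries. The documents do not support that: such a patient could stop TAF, stay in the study and be analysed. The protocol is not consistent here, since Section 6 also heads a paragraph with withdrawal from the product and then speaks of withdrawal from the study. This stands, and it makes exclusion possible rather than certain.

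**Other reports may show the event.** Section 7 requires all adverse events, serious or not, to be reported. Section 6 requires a report on each premature withdrawal, with its reasons and the last laboratory tests. A reader might infer that renal harm would vanish altogether; it need not. This is partial mitigation, because the creatinine and clearance summaries would still omit the patient.

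**The effect is small and the endpoint descriptive.** On the planned endpoint, the main illustration gives at most about 1 percentage point, within sampling error, in a study the protocol calls a pilot. This also stands, and it limits the weight of the point. It does not remove it: the error has a likely direction, a larger sample would not reduce it, and a description needs the right patients in it. A count of marked declines would show a sharper contrast (5/251 = 2.0% against 0/246), but the plan has no such count. Its absence is not an error, and Section 8 would permit one.

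**Conclusion.** The concern holds in a limited form. As written, the plan can remove patients with renal decline from the renal summaries although it provides for collecting their data, and no other rule restores them. Whether a given patient is removed depends on the investigator's judgment.

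The bias is favourable to TAF if decliners are withdrawn more often than others. That is plausible, but the documents do not establish it. Under the assumed inputs, mean change looks better by up to about 1 percentage point overall (five patients at -50%), or by 0.2 to 1.3 mL/min overall and 0.5 to 2.3 mL/min in a cohort of 33. The true size is unknown.

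The Section 8 sentence governs every endpoint, so a reader might infer that the primary viral suppression result is biased in the same way. This check covers the renal endpoint only, and nothing here measures an effect on the primary result. The change should be made, but it is not critical to the study's main result.

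**What to change.** Amend the population sentence in Section 8 for the renal analyses:

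- Include every patient who received TAF and has a baseline and at least one post-baseline creatinine.
- Use all values up to and including the ED visit, each at the month it was taken. Because the schedule in Section 5 shares one column for Month 24 and ED, state that ED values are not placed at Month 24.
- Add one summary: change from baseline to the last value on TAF.
- List values after the ED visit separately.
- Report the number withdrawn, with reasons, by prior-therapy cohort.

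The same amended sentence can sensibly apply to the other endpoints, which also avoids different population rules within one report. A new count of patients crossing a fixed threshold of clearance loss is not needed for this repair, and the documents give no basis for a cut-off.

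The cost is a little more analysis work on data the protocol already provides for; no visit or test is added. Patients with no post-baseline creatinine remain outside and should be counted and reported.
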